# 2.1.2. Secondary Objectives

- Characterize safety and tolerability of palbociclib and tamoxifen in first line therapy for subjects with HR(+)/HER2(-) advanced breast cancer who have not received prior systemic anti-cancer therapies for their advanced/metastatic disease.
- Evaluate response rates (complete or partial response) (RR) per local assessment and RECIST 1.1 or MDA criteria in subjects with HR(+)/HER2(-) advanced breast cancer who have not received prior systemic anti-cancer therapies for their advanced/metastatic disease treated with palbociclib in combination with tamoxifen.
- Evaluate clinical benefit rate RR (complete, partial response, or stable disease, lasting 24 weeks or longer) based on RECIST 1.1 or MDA criteria in subjects with HR(+)/HER2(-) advanced breast cancer who have not received prior systemic anti-cancer therapies for their advanced/metastatic disease treated with palbociclib in combination with tamoxifen.
- Measure overall survival (OS) at 2 years in subjects with HR(+)/HER2(-) advanced breast cancer who have not received prior systemic anti-cancer therapies for their advanced/metastatic disease treated with palbociclib in combination with tamoxifen.

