#### 5. TREATMENT PLAN

## 5.1. Overall Design and Study Plan

This is a non-randomized, open-label, single-arm, multicenter, phase II study of palbociclib in combination with tamoxifen in subjects with HR(+)/HER2(-) advanced breast cancer who have not received prior systemic anti-cancer therapies for their advanced/metastatic disease. The primary objective of the Phase II trial is to determine progression free survival (PFS) based on RECIST 1.1 Treatment will continue until disease progression, unacceptable toxicity, subject refusal, or subject death either from progression of disease, the therapy itself, or from other causes. Subjects, who voluntarily stop the study, have progressive disease, or unacceptable toxicities will be followed for a total of 24 months after discontinuation of study drug.

If funding is secured, correlative research analyses includes correlating alterations in circulating tumor DNA at the time of progression, correlating molecular alterations of genes associated with ER+ breast cancer in tumor tissue samples with clinical outcome and at the time of progression, comparing difference in response for subjects presenting with de novo metastatic breast cancer to subjects that progressed while on aromatase inhibitors, and comparing differences in response and toxicity profile in African American and Hispanic subjects to Caucasian subjects.

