# 7. STUDY CALENDAR & EVALUATIONS

[Cycle = 28 days]							T		
	Scree	ening	Cycle 1	Cycle 2	Cycle 3-5	Every 2 cycles	Every 3 cycles	Safety follow up	Long-Term follow up
Study Day	-28 days	-14 days	Day 1 	Day 1 (±3)	Day 1 (±3)	(± 7)	(± 7)	30 days (±7) post last study drug	Every 3 months (±14) for 2 years from registration
REQUIRED ASSESSMENTS									
Informed Consent/ HIPAA auth.	X								
Medical hx including prior therapies; pathology	X								
Physical examination	X		X	X	X	C7+		X	
Vital Signs, weight, height (screen only)	X		X	X	X	C7+		X	
ECOG status	X		X	X	X	C7+		X	
Baseline signs/ symptoms; AE assessment	X		X	X	X	C7+		$X^5$	
Concomitant medications	X		X	X	X	C7+		X	
Survival									$X^6$
LABORATORY TESTS									
Blood Chemistries 		X	X	X	X	C7+			
Platelets, ANC & Hgb 		X	D1, D15	D1, D15	X	C7+			
Pregnancy test for WOCP 		-72h	X	X	X	C7+			
DISEASE ASSESSMENT 						C3-19	C22+		
CT/MRI chest, abdomen/pelvis	X					$X^8$	$X^8$		X
CT or MRI Brain, if clinically indicated	X								
Whole body bone scan	X					$X^{8,9}$	$X^{8,9}$		
Bone x-ray, CT, or MRI 	X					$X^8$	$X^8$		
Skin color photography, if applicable	X					$X^8$	$X^8$		
TREATMENT EXPOSURE									
Palbociclib (Day 1-21)			X	X	$X^{16}$	$C7+^{16}$			
Tamoxifen (Continuous)			х —		—	C7+			
CORRELATIVE STUDIES (SPECIMEN COI	LLECTI	ION)					C8, 11, etc.		
Tumor tissue (unstained slides) 			X					$X^{11}$	
Blood for circulating tumor DNA 			X		C5		$X^{12}$	$X^{12}$	
BANKING SAMPLES (SPECIMEN COLLECTION)									
Whole Blood 			X						
Unstained Slides  (archival, if available)			X						
Serum and Plasma 			X					X	

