#### Footnotes:

- 1: For cycle 1 only: labs do not need to be repeated if done within 7 days of day 1.
- 2: Blood Chemistries to include: sodium, potassium, serum creatinine (or GFR; see 3.1.8), calcium, albumin, ALT, AST, bilirubin, alkaline phosphatase.
- 3: For Cycles 1 and 2 only, hematology assessments done on Day 1 and also on Day 15
- 4: A negative serum or urine pregnancy test is required within 72 hours of study registration and at the beginning of each cycle, if clinically indicated. If the urine test cannot be confirmed as negative, a serum pregnancy test will be required.
- 5: For subjects with unresolved treatment-related toxicity, follow as medically appropriate until resolution or stabilization
- 6: Survival assessment to be recorded every 3 months until 2 years from registration
- 7: Appropriate scans to assess disease status will be obtained within 28 days of study enrollment including CT chest, abdomen/pelvis. PET/CT: The CT portion of PET/CT is usually of lower quality and should typically not be used in place of dedicated diagnostic CT. However, if the CT portion is of diagnostic quality, it may be used.
- 8: Disease assessment will be performed on Day 1 of every 2 cycles starting at cycle 3 (ex. Day 1 of cycle 3, 5, 7, etc.) for the first 19 cycles (18 months). Disease assessment will be performed on Day 1 of every three cycles starting at cycle 22 (ex. Day 1 of cycle 22, 25, etc.) until discontinuation of study drug.
- 9: Bone scan will be repeated as per footnote 8 above only if positive for bone mets at the time of screening or if clinically indicated.
- 10: If bone lesion(s) detected from whole body bone scan, perform bone x-ray, CT or MRI of the largest bone metastatic area.
- 11: Histological confirmation of breast cancer diagnosis is required (Section 3.1.3). Although not required as a protocol procedure, a patient with a new metastatic lesion should be considered for biopsy whenever possible to reassess ER/PR/HER2 status, if clinically indicated. Also, biopsy at the time of progression should be considered as clinically indicated, but it is not required as a protocol procedure. If a biopsy is prospectively done as standard of care, the study would like to collect samples for correlative research. Unstained slides from either the fresh biopsy or from an archival tumor specimen (metastatic lesion) may be submitted at baseline.

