#### 7.5. Off Treatment

# 7.5.1. Protocol therapy discontinuation

A subject will be discontinued from the protocol therapy under the following circumstances:

- If there is evidence of disease progression
- If the treating physician thinks a change of therapy would be in the best interest of the subject
- If the subject requests to discontinue protocol therapy
- If the protocol therapy exhibits unacceptable toxicity
- If a female subject becomes pregnant

Subjects can stop study participation at any time. However, if they decide to stop, subjects will continue to be followed for survival for 24 months after discontinuation.

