# 7.7. Long Term Follow-up Evaluations (±14 days)

Subjects will continue to be followed for survival every 3 months for 24 months after registration.

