## 12.3. Sample Size

Study endpoint is progression free survival (PFS) as assessed by RECIST v1.1 criteria). Previous studies (31, 32) identified progression free survival with tamoxifen of 13 months in pre-menopausal women and 14.5 months in post-menopausal women in first line treatment for breast cancer. We use a null hypothesis of median PFS 15 months as a conservative choice and the alternative hypothesis of median PFS 25 months (31, 32). Controlling for a probability of one-sided Type I error of 0.05, the proposed sample size will be 48 to achieve an 80% statistical power for detecting this difference, assuming 20% censoring rate due to unevaluable, drop-out, and other lost-to-follow-up. The sample size analysis was conducted using the software PASS 14 (NCSS, Kaysville, Utah, USA.). The test was based on an exponential distribution assumption for single arm studies. The accrual period was assumed to be 24 months and the maximum follow-up 24 months too.

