### 12.5. Analysis of Secondary Endpoints

Characterize safety and tolerability of palbociclib and tamoxifen in first line therapy for subjects with HR(+)/HER2(-) advanced breast cancer who have not received prior systemic anti-cancer therapies for their advanced/metastatic disease.

 Proportion of subjects with each grade of adverse events as defined by CTCAE v4 will be computed along with 95% confidence intervals, and reported in a tabular and descriptive manner.

Assess response rate based on RECIST 1.1 or MDA Criteria. The response rate (complete or partial response) and 95% confidence interval for the response rate will be computed using PROC FREQ in SAS (Cary, NC).

Evaluate clinical benefit rate RR (complete, partial response, or stable disease) based on RECIST 1.1 or MDA Criteria in subjects with HR(+)/HER2(-) advanced breast cancer who have not received prior systemic anti-cancer therapies for their advanced/metastatic disease treated with palbociclib in combination with tamoxifen.

• Clinical benefit rate (complete, partial response, or stable disease) will be assessed every 8 weeks +/- 1 week while on study treatment using RECIST 1.1 (section 8) or MDA Criteria (for patients with bone only disease). Response will be recorded as disease control rate (DCR), or stable disease plus partial response plus complete response, and reported via waterfall plot. The response rate and 95% confidence interval for the response rate will be computed using PROC FREQ in SAS (Cary, NC).

Measure 2-year overall survival (OS) in subjects with HR(+)/HER2(-) advanced breast cancer who have not received prior systemic anti-cancer therapies for their advanced/metastatic disease treated with palbociclib in combination with tamoxifen.

Median OS times will be computed, and OS rate will be calculated with associated 95% confidence intervals. Kaplan-Meier curves will be plotted. Data will be analyzed using the PROC FREQ and PROC LIFETEST in SAS.

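### Two survival follow-up clocks conflict; under the 24-months-from-registration clock, median OS is unlikely to be reached if the drug works as hypothesised, and the curve after month 24 is biased upward

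*Combined protocol and SAP*

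**What the plan says.** All references are to the combined protocol and SAP.

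- **Objective (2.1.2):** "Measure overall survival (OS) at 2 years in subjects with HR(+)/HER2(-) advanced breast cancer".
- **Analysis (12.5):** "Median OS times will be computed, and OS rate will be calculated with associated 95% confidence intervals". Kaplan-Meier curves are also planned, and both PROC FREQ and PROC LIFETEST are named. No OS start date, OS censoring rule or truncation of the curve is given.
- **Clock counted from registration:** the calendar header in section 7 has "Every 3 months (±14) for 2 years from registration", footnote 6 has "Survival assessment to be recorded every 3 months until 2 years from registration", and section 7.7 has "Subjects will continue to be followed for survival every 3 months for 24 months after registration".
- **Clock counted from stopping drug:** section 5.1 says that subjects who stop voluntarily, progress or have unacceptable toxicity "will be followed for a total of 24 months after discontinuation of study drug". Section 7.5.1, on subjects who decide to stop, says "subjects will continue to be followed for survival for 24 months after discontinuation".
- **Subjects still on drug:** under section 7.4, disease assessment continues every three cycles from cycle 22 until drug is stopped, so these subjects stay under observation past month 24.
- **Design (12.3 and synopsis):** 48 subjects, null median PFS 15 months, and "the alternative hypothesis of median PFS 25 months". Accrual is 24 months, follow-up 24 months and total duration an estimated 48 months.

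**The concern.** The two clocks give different OS data sets. A subject who progresses at month 6 is followed to month 24 under one and to month 30 under the other. A subject who stops drug at month 30 has only the 30-day safety visit left under the first, but two more years under the second.

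Under the registration clock there are two further problems. The planned median probably lies outside the observation window if the treatment performs as designed. And after month 24 the risk set consists only of subjects who have not yet stopped drug. Progressed subjects, who are closest to death, have been dropped. That censoring is informative, so a curve drawn through all available data would show a plateau produced by who is still being watched. A reader would take it for long survival.

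**Working it through.** **Design inputs.** The documents give no OS assumption to reproduce, so I first checked that I read the design as the plan does.
- Events needed = (1.645 + 0.842)² / [ln(25/15)]² = 23.7, so 24.
- With hazard λ = ln 2/25 = 0.0277, 24 months of uniform accrual and 24 further months, P(event) = 1 − (e^(−24λ) − e^(−48λ))/(24λ) = 1 − (0.514 − 0.264)/0.665 = 0.625.
- N = 23.7/0.625 = 37.9, and 38/0.8 = 47.5, so 48. This matches the plan, with data running to study month 48.

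**Bound that needs no outside figure (registration clock).**
- Alternative: PFS(24) = 0.5^(24/25) = 0.514. OS(24) must be at least this, so true median OS exceeds 24 months.
- Even if every progression were an immediate death, P(at least 24 of 48 die by month 24), binomial with p = 0.486 and no loss, is 0.48. That is the ceiling.
- Null: PFS(24) = 0.5^(24/15) = 0.330. A median OS at or below 24 months is not excluded.

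**Chance that the Kaplan-Meier median is reached.** Simulation of 4,000 trials per row: n = 48, uniform entry over 24 months, exponential PFS plus exponential post-progression survival, drug stopped at progression, no other loss. Median post-progression survival is an assumption.

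| Median PFS | Assumed median post-progression survival | True median OS | True OS(24) | Registration clock, all cut at month 24 | Discontinuation clock, run to completion | Discontinuation clock, cut at study month 48 |
|---|---|---|---|---|---|---|
| 15 | 6 | 24.4 | 0.51 | 0.50 | 1.00 | 1.00 |
| 15 | 12 | 32.5 | 0.65 | 0.02 | 1.00 | 0.91 |
| 15 | 18 | 39.8 | 0.73 | <0.01 | 1.00 | 0.57 |
| 15 | 24 | 46.6 | 0.79 | 0 | 0.99 | 0.32 |
| 25 | 6 | 34.4 | 0.66 | 0.02 | 1.00 | 0.87 |
| 25 | 12 | 43.6 | 0.76 | <0.01 | 1.00 | 0.47 |
| 25 | 18 | 51.7 | 0.81 | 0 | 1.00 | 0.20 |
| 25 | 24 | 59.2 | 0.85 | 0 | 1.00 | 0.10 |

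**Registration clock using all available data.** Each subject is observed to the later of month 24 and one month after stopping drug, with everything cut at study month 48. Assumed post-progression medians are 12, 18 and 24 months, with 3,000 trials each.
- Median reached: about 1 to 10% of trials at median PFS 15, and under 2% at median PFS 25.
- Deaths after month 24 and before study month 48: 5.9 to 9.3 expected, of which 0.2 to 0.4 are recorded.
- Average Kaplan-Meier estimate at 36 months across scenarios: 0.63 to 0.84, against a true 0.45 to 0.73. The excess is 0.63 − 0.45 = 0.18 at one end and 0.84 − 0.73 = 0.11 at the other.
- With vital status collected on everyone to study month 48, the median is reached in 45 to 96% of trials (PFS 15) and 14 to 58% (PFS 25).

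The estimate at month 24 itself uses only data up to month 24, so this bias does not touch it.

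**The ±14-day window.** If every last contact fell 14 days early (0.46 month), the deaths missed are S(23.54) − S(24). For exponential OS medians from 60 down to 24 months this is 0.4 to 0.7 percentage points, or 0.2 to 0.3 deaths of 48. The 95% CI half-width is 12 to 14 points.

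**The case against.** The stated objective is 2-year OS, and 12.5 already plans a rate with a CI and Kaplan-Meier curves. The median is descriptive, no decision hangs on it, and a result of not reached is honest. That stands, and it keeps the point a secondary one. It does not answer the bias in the curve beyond month 24.

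The documents state no OS censoring rule, so the biased curve depends on how the analyst would censor. That is also fair: if everyone were censored at 24 months, the bias would vanish. But nothing in 12.5 says so, and the data on subjects still on drug will be there to use.

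Three stronger readings are tempting, and the documents do not support them.

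- *Survival follow-up simply stops at 2 years from registration.* Sections 5.1 and 7.5.1 say otherwise. Under their clock there is little bias, and the median is reached in about 10 to 90% of trials within 48 months (post-progression medians of 12 to 24 months).
- *Median OS cannot be observed.* Under the null it can, even on the registration clock. With an assumed post-progression median of 6 months it is reached in about 50% of trials when all are cut at month 24, and in nearly 70% when later on-drug data are used.
- *The visit window undermines the 2-year rate.* It moves the Kaplan-Meier rate by under about 1 percentage point. It matters mainly for a crude PROC FREQ proportion, which would need a rule for subjects last seen just before the landmark.

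**Conclusion.** The point holds in limited form. The contradiction between the two clocks is certain from the text. That true median OS lies beyond 24 months under the design alternative follows from the plan's own figures, as does the ceiling of about 0.48 on reaching it under the registration clock.

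The lower probabilities and the upward bias of about 11 to 18 points at 36 months depend on three assumptions: post-progression median survival of 12 to 24 months, drug stopped at progression, and an analysis that uses all available data. The primary PFS test is unaffected, and the 24-month OS rate can be estimated under either clock. The change should be made because it is nearly free and removes a real source of misreading from a named secondary endpoint.

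**What to change.** 1. Reconcile sections 5.1 and 7.5.1 with the calendar, footnote 6 and section 7.7 into one survival follow-up clock that applies to all subjects, on or off drug.
2. In 12.5, define the OS start date and censoring rule, and make the OS estimate the 24-month Kaplan-Meier rate with 95% CI from PROC LIFETEST, not a crude PROC FREQ proportion.
3. If the registration clock is kept, censor every subject administratively at 24 months and drop median OS. Report median OS and the later curve only if vital status is collected on all subjects to a common cut-off, such as the planned 48-month study end.
4. As a minor tidy-up, place the final survival contact on or after the 2-year date (0 to +14 days).

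The cost is wording. If the longer follow-up is chosen, add vital-status checks within the 48 months already planned. Even then the median may not be reached: the simulation gives 14 to 58% under the design alternative.

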### 12.6. Analysis of Correlative Endpoints, if funding is secured

- Perform proteomic analysis of plasma exosomes to identify potential mechanisms of primary and secondary resistance to tamoxifen/palbociclib.
- Analyze tumor specimens for protein expression of candidate markers of primary resistance.
- Compare difference in response for subjects presenting with de novo metastatic breast cancer to subjects that progressed while on aromatase inhibitors
- Compare differences in response and toxicity profile in African American and Hispanic subjects to Caucasian subjects
- Compare differences in response and toxicity profile between pre- and post-menopausal women.

#### 13. TRIAL MANAGEMENT

## 13.1. Study Monitoring

Monitoring visits to the trial sites will be made periodically during the trial to ensure key aspects of the protocol are followed. For-cause visits may occur as necessary. Source documents will be reviewed for verification of agreement with data entered into OnCore®. It is important for the site investigator and their relevant personnel to be available for a sufficient amount of time during the monitoring visits or audit, if applicable. The site investigator and institution guarantee access to source documents by BTCRC AHQ or its designee.

Remote validation of Oncore® data will be completed on a continual basis throughout the life cycle of the study. Automated edit check listings will be used to generate queries in the EDC system and transmitted to the site to address in a timely fashion. Corrections will be made by the study site personnel.

The trial site may also be subject to quality assurance audit by Pfizer or its designee as well as inspection by appropriate regulatory agencies.

## 13.2. Data and Safety Monitoring Plan

The study will be conducted in accordance with the University of Illinois Cancer Center's Data and Safety Monitoring Plan. The University of Illinois Cancer Center Data Safety Monitoring Committee (DSMC) will review and make recommendations on this trial. BTCRC AHQ will provide the University of Illinois Cancer Center DSMC with periodic data reports to comply with the UICC DSMC review requirements.

In addition, BTCRC AHQ data and safety monitoring activities include:

- Review of all adverse events requiring expedited reporting as defined in the protocol
- Notify participating sites of adverse events requiring expedited reporting
- Provide the Sponsor Investigator with trial accrual progress and safety information
- Provide data summary reports to the sponsor-investigator
- Provide data summary reports to the lead institution's Data Safety Monitoring Committee for review as per their DSMP.

### **Data and Safety Monitoring and Reporting Guidelines**

BTCRC AHQ will compile data summary reports for this trial and submit these reports monthly to the Sponsor Investigator. BTCRC AHQ will submit data summary reports at minimum twice per year for review by the University of Illinois Cancer Center Data Safety Monitoring Committee (DSMC).

### 13.3. Amendments

If it is necessary for the study protocol to be amended and/or the informed consent revised, the amendment or a new version of the study protocol (amended protocol) and/or the revised informed consent will be generated by BTCRC AHQ and must be approved by the sponsor-investigator, Pfizer (if required by the contract), the FDA (if applicable), and each site's IRB.

The site investigator is responsible for the distribution of these documents to his or her IRB, and to the staff at his or her center.

## 13.4. Compliance with Trial Registration and Results Posting Requirements

Under the terms of the Food and Drug Administration Modernization Act (FDAMA) and the Food and Drug Administration Amendments Act (FDAAA), the sponsor-investigator of the trial is solely responsible for determining whether the trial and its results are subject to the requirements for submission to the Clinical Trials Data Bank, http://www.clinicaltrials.gov. The sponsor-investigator has delegated responsibility to BTCRC AHQ for registering the trial and posting the results on clinicaltrials.gov. Information posted will allow subjects to identify potentially appropriate trials for their disease conditions and pursue participation by calling a central contact number for further information on appropriate trial locations and study site contact information.

#### 14. DATA HANDLING AND RECORD KEEPING

#### 14.1. Data Management

BTCRC AHQ will serve as the Clinical Research Office for this trial. Data will be collected through a web based clinical research platform, OnCore®, a system compliant with Good Clinical Practices and Federal Rules and Regulations. BTCRC AHQ personnel will coordinate and manage data for quality control assurance and integrity. All data will be collected and entered into OnCore® by study site personnel from participating institutions.

